| Diagnostic Assessments | | | | | |
| Clinician Administered PTSD Scale for DSM-V: Past-Month Version (CAPS-5) | X | | | | |
| Structured Clinical Interview for DSM-5 Disorders-Research Version (SCID-5-RV) | X | | | | |
| Life Events Checklist-5 (LEC) | X | | | | |
| Primary Outcome Measures: Self-Report | | | | | |
| State Trait Anger Expression Inventory-2 (STAXI-2) | X | X | X | X | X |
| Buss-Perry Aggression Questionnaire (BPAQ) | X | X | X | X | X |
| Primary Outcome Measure: Experimental | | | | | |
| Taylor Reaction Time Task (TRT) | | | | X | |
| Secondary Outcome Measures | | | | | |
| Physiological Reactivity: Heart Rate, Skin Conductance | | | | X | |
| Emotion Regulation: State Difficulties in Emotion Regulation Scale (DERS-S) | | | | X | |
| Exploratory Outcome Measures | | | | | |
| Five Facet Mindfulness Questionnaire (FFMQ) | X | X | X | X | X |
| PTSD Checklist for the DSM-V (PCL-5) | X | X | X | X | X |
| Quantity-Frequency Variability Index (QFI) | X | X | X | X | X |
| Alcohol Dependency Scale (ADS) | X | X | X | X | X |

Baseline Session:

(a) PTSD, other psychiatric disorders, anger and aggression:

The DSM-V criteria for PTSD will be established using the Clinician Administered PTSD Scale: Past-Month Version (CAPS-5, Weathers et al., 2013a). The CAPS-5 will be used to confirm DSM-V PTSD diagnosis and to provide a continuous measure of PTSD severity (CAPS-5 total score). To facilitate the administration of the CAPS, participants will also complete the Life Events Checklist-5 (LEC; Weathers et al., 2013b), which is a self-report questionnaire used to assess the extent to which individuals experienced any of 17 different stressful or difficult life events (e.g., combat exposure, natural disaster, fire or explosion).

Participants will be assessed for psychiatric disorders at the baseline session using the Structured Clinical Interview for DSM-5 Disorders – Research Version (SCID-5-RV, First et al.,

2014). The information from the SCID will be used to exclude participants with severe psychiatric disorders (e.g., schizophrenia or bipolar disorder).

(b) Battery of Self-Report Questionnaires: Participants will also complete a battery of self-report questionnaires including assessments measuring anger and aggression, in addition to trait mindfulness, PTSD, and alcohol use:

- State Trait Anger Expression Inventory-2 (STAXI-2, Spielberger, 1999)
- Buss-Perry Aggression Questionnaire (BPAG; Buss and Perry, 1992)

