The mean level of each physiologic variable (HR, SCL) will be computed for the last 30 seconds of the baseline (B) segment, for each of the two 30-second blocks during the 60-second trauma reading (TR), for each of the two 30-second blocks during the 60-second trauma imagery (TI) segments, and for the last 30-seconds of the resting (R) segment. Response (change scores) will be calculated by subtracting the baseline (B) value from the peak value of the four 30-

second blocks from the trauma imagery/trauma reading segments (TR/TI). Change scores also will be calculated by subtracting the peak trauma imagery/trauma reading value (TR/TI) from the resting period (R) value.

As a manipulation check, after the resting period (R), participants will complete a brief assessment to indicate how vivid the imagery was, their perceived arousal, the subjective pleasantness, and their sense of control. Participants also will be asked to rate the extent to which they experienced 6 discrete emotions (happiness, sadness, fear, surprise, anger, and disgust). Participants will be asked to rate their responses using a 12-point Likert-type scale ranging from 0 (not at all) to 12 (very much).

(d) State Emotion Regulation: State emotion regulation will be assessed using the State Difficulties in Emotion Regulation Scale (DERS-S, McLaughlin et al., 2007). This measure will be completed by participants following the trauma reading/trauma imagery (TR/TI; pre-task), and again following the resting period (R; post-task).

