Primary Aim 1 Hypothesis 1.1: Participants assigned to MBSR will report decreased levels of self-reported anger and aggression at post-treatment and at the 3-month follow up compared to those assigned to the TREC group. Scores on the State Trait Anger Expression Inventory-2 and the Buss-Perry Aggression Questionnaire will be used as the primary outcome variables for self-report anger and aggression. Intent-to-treat analyses will be conducted for these outcomes, which will be examined separately. Bonferroni adjustments will be implemented to control for Type 1 error. These data will be analyzed using mixed effects models with treatment, time, and treatment x time interaction as fixed effects. Subject will be the clustering factor and it will be nested within therapy group which will also be considered random. Different variance-covariance structures will be considered and the best one selected based on Schwartz’ Bayesian Information Criterion (BIC). Mixed effects models are the preferred method for analyses of such data as they use all available data on an individual, give unbiased results under general missing data assumptions and provide flexibility in modeling the correlation structure within subject. Significant interactions will be examined further using post-hoc tests.

Primary Aim 1, Hypothesis 1.2: Participants assigned to MBSR will exhibit lower levels of anger and aggression on the TRT compared to those assigned to the TREC group. Mixed effects models will be used to compare the TREC group to the MBSR group on responses on the TRT: (1) mean shock level across the TRT, and (2) total number of “20” shocks chosen on the TRT following the same strategy as for primary aim 1 hypothesis 1.1.

Secondary Aim 1, Hypothesis 1.1: Those assigned to MBSR will exhibit significant decreases in HR and SCL and increases in emotion regulation compared to those assigned to the TREC group. Mixed effects models will be used to compare the TREC group to the MBSR group on physiological variables (HR, SCL) and emotion regulation (DERS-S) following the same strategy as for primary aim 1, hypothesis 1.1.

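### The TRT is measured once, so the treatment-by-time model assigned to it cannot be fitted; heart rate, skin conductance and DERS-S need a named within-session contrast, and the secondary hypotheses need rewording

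*Combined protocol and SAP*

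**What the plan says.** - **Reference strategy.** Data Analyses, Primary Aim 1, Hypothesis 1.1 fits STAXI-2 and BPAQ with treatment, time and treatment by time as fixed effects. Subject is nested in therapy group and both are random. The covariance structure is chosen by BIC, and significant interactions are followed by post-hoc tests.
- **TRT.** Hypothesis 1.2 predicts less TRT aggression under MBSR than under TREC. Both outcomes, mean shock level and number of '20' shocks, are analysed "chosen on the TRT following the same strategy as for primary aim 1 hypothesis 1.1".
- **Secondary measures.** Secondary Aim 1, Hypothesis 1.1 uses the same strategy and predicts: "Those assigned to MBSR will exhibit significant decreases in HR and SCL and increases in emotion regulation". Secondary Hypothesis 1.2 correlates changes in these measures with TRT responses within MBSR, and describes the TRT result as a decrease.
- **Schedule.** The visits in Table 1 are baseline, week 3, week 6, post-treatment and 3-month follow-up. The rows read "Taylor Reaction Time Task (TRT) | | | | X", "Physiological Reactivity: Heart Rate, Skin Conductance | | | | X" and "Emotion Regulation: State Difficulties in Emotion Regulation Scale (DERS-S) | | | | X". In each, the only mark falls at post-treatment.
- **Inside that session.** Under Psychophysiological Assessments, "The mean level of each physiologic variable (HR, SCL) will be computed for the last 30 seconds of the baseline (B) segment", and also for two reading blocks, two imagery blocks and the end of the rest period. Two contrasts are defined: "Response (change scores) will be calculated by subtracting the baseline (B) value from the peak value" and "Change scores also will be calculated by subtracting the peak trauma imagery/trauma reading value (TR/TI) from the resting period (R) value". DERS-S is given after the script and imagery and again after the rest.
- **General provisions.** The opening of Data Analyses allows transformations for non-normal data, controls for medication use (yes/no) in every analysis, and adds as covariates any variables on which the arms are found to differ.

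**The concern.** A model with a time factor needs at least two occasions, and the TRT has one. The interaction that tests the treatment effect under Hypothesis 1.1, the post-hoc tests that follow it and the BIC choice of covariance structure have nothing to work on for this primary outcome. Somebody will have to write a different model, and if that happens after the data are in, the covariates and the handling of the count will be chosen with the results within reach.

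For heart rate, skin conductance and DERS-S the difficulty is different. A model can be fitted, but the plan does not say what time means for them or which score carries the test. Sample Size and Power Considerations intends to use within-session difference scores for these measures to size a larger trial, so the ambiguity would carry into that calculation.

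Finally, a reader will naturally take decreases and increases after an eight-week treatment to mean change from before it. No such change is measured for any of these variables.

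**Working it through.** The plan gives no power, effect size or alpha behind its 60 participants, so there is no figure to reproduce. The check is whether each model can be estimated from the schedule.

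**Inputs.** 60 participants (Inclusion Criteria); allocation in groups of 6 (Randomization Procedures); occasions from Table 1 and from the description of the post-treatment session; 28 TRT trials with a shock choice before each (Aggression).

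**1. Fixed effects for the TRT.** The strategy needs columns for intercept, arm, time and arm by time. When every record is post-treatment, time equals 1 throughout and the interaction equals arm. The columns are then 1, A, 1, A: rank 2 of 4. Only the intercept and the arm effect can be estimated.

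**2. Random effects for the TRT.** With one record per participant, subject variance and residual variance both multiply the identity matrix, so only their sum is identified. Two of the three components (therapy group, subject, residual) can be separated.

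**3. The same check for the other measures.** T occasions need 2 × T fixed-effect columns.

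| Measure | Occasions | Columns | Rank |
|---|---|---|---|
| STAXI-2, BPAQ | 5 visits | 10 | 10 |
| Heart rate, skin conductance | 6 within-session values | 12 | 12 |
| DERS-S | 2 within-session values | 4 | 4 |

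With two or more values per participant, all three variance components are identified. The failure is therefore specific to the TRT.

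**4. What remains for the TRT.** 60 / 6 = 10 therapy groups, and 10 − 2 = 8 between-group degrees of freedom for the arm comparison. A model with arm and a random therapy group can be estimated. Three participant-level covariates (medication, BPAQ, trait anger) draw mainly on the 60 − 10 = 50 within-group degrees of freedom. If baseline BPAQ correlates 0.3 to 0.4 with TRT shock level (an assumption; the documents cite an association but give no coefficient), adjustment removes r² = 0.09 to 0.16 of the variance.

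**5. The '20'-shock count.** It runs from 0 to 28, and the documents give no rate. For a negative binomial with mean μ and size k, P(0) = (k/(k+μ))^k and variance/mean = 1 + μ/k. Assuming μ from 0.5 to 4 and k from 0.3 to 1.0, zeros range from 20% (μ = 4, k = 1) to 75% (μ = 0.5, k = 0.3), and variance/mean from 1.5 to 14.3. No transformation spreads out a pile of identical zeros.

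Simulated power with 30 per arm, no clustering, counts capped at 28 and 3,000 replicates, where α = 1/k:

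| Assumed means | α | Linear comparison | Negative binomial |
|---|---|---|---|
| 2.0 vs 0.6 | 3 | 0.54 | 0.63 |
| 1.5 vs 0.4 | 2 | 0.72 | 0.79 |
| 2 vs 1 | 3 | 0.22 | 0.28 |
| 2 vs 1 | 2 | 0.31 | 0.36 |

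Across the simulations run, type 1 error was 0.03 to 0.047 for the linear comparison and 0.047 to 0.065 for the negative-binomial likelihood-ratio test. Part of the apparent gain therefore comes from a slightly liberal test.

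**6. Change over treatment.** TRT, heart rate, skin conductance and DERS-S are absent from the baseline, interim and follow-up batteries. A pre-to-post difference needs two visits, and each measure has one. DERS-S has no value before the script either, so its two administrations can show recovery after the script but not reactivity to it.

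**The case against.** The best defence is that the intention is clear. Hypothesis 1.2 says the models compare the two arms, and a competent analyst would drop the time terms and fit arm with a random therapy group. This is also a pilot that does not promise significance. Much of that stands: the gap is in specification and is easily closed. But small size excuses low power, not a primary model that cannot be run as written.

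Four stronger readings are tempting, and the documents do not support them.

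- **A reader might infer that heart rate, skin conductance and DERS-S have no time factor and no baseline either.** They have six and two within-session values, with reactivity and recovery scores defined for the physiological measures. Treatment by segment can be estimated, and decreases could have been meant within the session. What is missing is the choice of contrast.
- **A reader might infer that Hypothesis 1.2 is untestable.** It predicts a lower level than in TREC, which a randomised post-treatment comparison can test. The wording about a decrease on the TRT is in Secondary Hypothesis 1.2.
- **A reader might infer that the TRT comparison would be unadjusted.** Medication use is a planned control throughout, and variables found to be imbalanced are added. The weakness is that baseline BPAQ and trait anger enter only if a check after randomisation selects them, when few units are randomised.
- **A reader might infer that a linear analysis of the '20' shocks is invalid.** The simulations show no type 1 error inflation for it, the plan allows transformation, and the term mixed effects models does not exclude a generalised model, although none is named.

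**Conclusion.** The point holds for the TRT without any assumption: the time effect, the interaction and a separate subject variance cannot be estimated from one occasion. The model for Hypothesis 1.2 must be replaced before analysis. Its wording needs no change.

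For heart rate, skin conductance and DERS-S the defect is an undefined contrast, not an unfittable model. For all the post-treatment-only measures, no change from before treatment exists, so the secondary hypotheses claim more than the schedule can show if read that way.

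The figure of about 8 degrees of freedom assumes that 10 groups of 6 are actually formed. The 9% to 16% variance reduction rests on an assumed correlation. The count-model gain of 5 to 9 percentage points in the table rests on assumed event rates and dispersion, ignores clustering, and nearly vanishes when dispersion is low. It is a gain in efficiency and interpretability, secondary to the model defect.

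**What to change.** 1. **Hypothesis 1.2, mean shock level.** Replace the reference to the Hypothesis 1.1 strategy with a post-treatment linear mixed model: arm, the planned medication control, baseline BPAQ and baseline STAXI-2 trait anger as prespecified fixed effects, and therapy group as a random effect. State a small-sample rule for the arm test based on between-group degrees of freedom (about 8), and keep it even if the estimated group variance is zero.
2. **Hypothesis 1.2, '20' shocks.** Use the same predictors in an overdispersed count model, or a binomial model out of 28, with a random therapy group. Report a rate ratio or odds ratio with its interval, and name a small-sample reference for the test, because large-sample tests can be liberal with so few groups.
3. **Secondary Hypothesis 1.1.** State which quantity is tested for heart rate and skin conductance: reactivity (peak reading/imagery value minus B), recovery (R minus peak), or treatment by segment. State which DERS-S administration, or the change between the two, is used. Use the same definitions in Secondary Hypothesis 1.2 and in the effect-size calculation for the later trial.
4. **Wording.** In Secondary Hypothesis 1.1, replace decreases and increases with between-arm differences at the post-treatment session. In Secondary Hypothesis 1.2, describe associations within MBSR at that session. Leave Hypothesis 1.2 as worded.

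No new data are needed, as every covariate is already collected. The cost is a few degrees of freedom, and conclusions for these measures narrow to post-treatment differences or associations.

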Although anger and aggression are commonly observed in military veterans with PTSD, there are few interventions that have been developed and tested to treat anger and aggression in this population. Mindfulness may be one such treatment that would be particularly useful in decreasing anger and aggression as it could (1) more effectively target the PTSD-specific symptoms most strongly associated with aggression, (2) assist veterans with PTSD in achieving awareness and insight into their anger states, which is important for the regulation of anger and aggressive reactions, and (3) be easily implemented and would not require a large time commitment from individuals. Findings showing that MBSR is effective in reducing anger and aggressive behavior in veterans with PTSD would be important as it could be an additional treatment that could be offered to veterans with PTSD who are struggling with these problems. Such an intervention could help decrease anger and prevent the perpetration of aggression among veterans with PTSD, thus preventing the detrimental consequences that anger and aggression can have on the lives of veterans, their families, and society at large.

Research Plan:

Overview: The proposed project will examine whether Mindfulness Based Stress Reduction (MBSR) decreases anger and aggression in veterans with PTSD. This project also will examine two potential mechanisms of action of MBSR: physiological reactivity and emotion regulation. This project will examine the initial efficacy of MBSR in a pilot randomized controlled study with 60 veterans with PTSD experiencing problems with anger and aggression. Participants will attend a baseline laboratory session to assess initial levels of self-reported anger and aggression and will then be randomly assigned to participate in a group PTSD psychoeducational course (the Trauma Recovery Education Course (TREC)) or group MBSR. After completing TREC or MBSR, all participants will participate in a post-treatment laboratory session in which self-reported anger and aggression will be assessed. In addition, during the laboratory session, participants will complete an experimental portion where they will be exposed to trauma-related stimuli, followed by participation in an experimental paradigm designed to assess aggressive behavior. After completing the post-treatment session, all participants will attend a 3-month follow-up session to assess long-term gains in the management of anger and aggression.

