Participants:

[figure not shown]
Inclusion Criteria: We will enroll 60 veterans with PTSD. To be eligible for the study, participants must meet current DSM-V diagnostic criteria for PTSD (American Psychiatric Association, 2013). PTSD will be established by interview using the Clinician Administered Posttraumatic Stress Disorder Scale for the DSM-V (CAPS-5; Weathers et al., 2013a). Participants must also indicate current difficulties with anger and aggression as indicated by a score of 20 or higher on the trait anger scale of the State Trait Anger Expression Inventory-2 (STAXI-2, Spielberger, 1999), indicating moderate to severe anger problems. Veterans from all eras will be eligible to participate.

Exclusion Criteria: Participants with a current diagnosis of bipolar disorder, psychotic disorder, or current substance use disorder with severe symptoms. Participants also must not have a seizure disorder and must not be taking any medications that would affect cognition or behavior on the aggression task, including pain medication, benzodiazepines, or antipsychotics. Participants also must not have a positive drug (e.g., amphetamine, opiates, and cocaine) or alcohol urine screen at the post-treatment session (see below), as these substances could affect performance on the study tasks implemented at that session. Finally, participants must not currently be receiving concurrent individual therapy or group therapy focused on anger and aggression and must not currently be participating in the modified TREC group offered at the West Haven VA (WHVA).

Research Design and Methods

For an overview of the time line for study procedures, see Figure 2.

Figure 2. Timeline of Study Procedures

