Trauma Scripting Procedure. After completing the diagnostic interviews (CAPS-5/SCID-5-RV), eligible participants will participate in a trauma-script development procedure as part of a well-validated, script-driven trauma imagery task (Pitman et al., 1987). For this procedure, participants will be asked to identify their most traumatic experience. If they identify more than one event, they will be asked to choose the one that they consider the most distressing. They will first be asked to describe the experience in writing using a script preparation form and then will be asked to indicate which of several different subjective visceral and muscular reactions (e.g., heart beating slower/faster, feeling sweaty, stomach in knots, feeling warm, hands trembling, tension in arms, nausea) may have accompanied the experience. Participants’ written responses will then be reviewed and they will be asked to clarify or expand on the details if necessary. After the session, a script lasting approximately 60 seconds in duration will be composed that portrays the traumatic experience in the second person, present tense, and incorporates the different visceral or muscular reactions. The script will then be audio recorded for playback

during the experimental portion of the post-treatment session. A research assistant (who will be named later upon being hired) will read the narrative scripts to be audio-recorded.

During this baseline session, participants will also complete a battery of self-report questionnaires (see below for full details) to assess baseline levels of anger and aggression.

Randomization Procedures. After participants have completed the Baseline Screening and Evaluation Session they will be randomized to either the TREC group or the MBSR group. To decrease the amount of time participants have to wait before starting group treatment, randomization will be implemented at the group level. That is, after 6 participants are recruited, they will be randomly assigned using urn randomization procedures, to either the TREC group or the MBSR group.

Post-treatment Session: After all participants have completed their assigned interventions (TREC or MBSR) they will be scheduled for the post-treatment session to be held in the biological studies laboratory at the WHVA. At this session, all participants will complete a battery of self-report questionnaires to assess post-treatment levels of anger and aggression (see below).

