Secondary Aim 1, Hypothesis 1.2: Within the MBSR group, decreases in physiological reactivity and increases in emotion regulation will be associated with decreases in aggression on the TRT. Pearson product moment correlations will be calculated to examine the association between changes in HR, SC, and emotion regulation and the TRT responses (i.e., mean shock level across the TRT and total number of “20” shocks chosen on the TRT).

Sample Size and Power Considerations

Although the proposed sample size may not be sufficient in establishing statistical significance but rather a pattern of results that suggest promising effects across anger outcomes, it is important to emphasize that the fundamental purpose of the pilot trial is to provide information for the planning of a future large scale clinical trial examining the efficacy of MBSR in decreasing anger and aggression in veterans with PTSD and examining additional mechanisms of action (i.e., behavioral, cognitive, social, biological) that lead to behavior change. To that end, the pilot RCT data will be used in power calculations to calculate the sample size for a later full-scale RCT examining MBSR for anger and aggression for veterans with PTSD.

Effect sizes for determining the sample size for the larger RCT will be calculated based on differences between the baseline and post-treatment scores on the self-report measures of

anger and aggression (STAXI-2, BPAQ), as well as the difference scores between the physiological measures (i.e., HR and SC) and emotion regulation obtained during the experimental portion of the post-treatment session. Comparisons will be made using a two-sample t-test. Due to the possibility that estimation of effect sizes based on pilot studies may be inaccurate (Kraemer et al., 2006), we will implement procedures recommended for improved characterization of effect sizes derived from pilot studies (Thabane et al., 2010). These include close consultation with clinicians who have used the treatment (i.e., [name]), and accounting for the effect size uncertainty by constructing confidence intervals around the observed effect size.

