Due to the nature of group treatment, additional considerations related to sample size will need to be considered given that a portion of the variance in treatment effects will be accounted for by clustering of effects within a particular group. Clustering group effects can be measured by an intra-class correlation ρ , which is defined as the ratio of variance due to the clustering variable relative to the total variance (cluster and error) (Schnurr et al., 2001). Once ρ has been determined, the adjusted sample size can be determined using the following formula: $m = n * N / (1 + (n - 1) \rho)$, where m is the effective number of independent observations after accounting for interclass correlation; n is the number of repeated measures per group; and N is the base sample size needed to detect the effect.

References:

- American Psychiatric Association (2013). *Diagnostic and statistical manual of mental disorders* (5th ed.) Arlington, VA: American Psychiatric Publishing.
- Anderson, C.A., & Bushman, B.J. (1997). External validity of 'trivial' experiments: The case of laboratory aggression. *Review of General Psychology*, 1, 19-41.
- Anderson, C.A., & Bushman, B.J. (2001). Effects of violent video games on aggressive behavior, aggressive cognition, aggressive affect, physiological arousal, and prosocial behavior: A meta-analytic review of the scientific literature. *Psychological Science*, 12, 353-359.
- Baer, R.A. (2003). Mindfulness training as a clinical intervention. *Clinical Psychology: Science and Practice*, 10, 125-143.
- Ben-Porath, D.D. & Taylor, S.P. (2002). The effects of diazepam (valium) and aggressive disposition on human aggression: An experimental investigation. *Addictive Behavior*, 27, 167-177.

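### The only analysis linking the proposed mechanisms to laboratory aggression is a one-session correlation within the MBSR arm, which is the same whether or not MBSR shifts the mechanism

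*Combined protocol and SAP*

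**What the plan says.** Research Plan, Overview: "This project also will examine two potential mechanisms of action of MBSR: physiological reactivity and emotion regulation".

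In Data Analyses, Hypothesis 1.2 of Secondary Aim 1 reads as follows: "Within the MBSR group, decreases in physiological reactivity and increases in emotion regulation will be associated with decreases in aggression on the TRT". The method is: "Pearson product moment correlations will be calculated to examine the association between changes in HR, SC, and emotion regulation and the TRT responses". The two TRT responses are the average shock setting and the number of level-20 shocks chosen.

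Table 1 schedules the TRT, heart rate, skin conductance and DERS-S at post-treatment only. The Psychophysiological Assessments section defines two scores for heart rate and skin conductance: peak during script and imagery minus the pre-script baseline, and rest minus peak. The DERS-S is given twice, both times in that same session.

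For Primary Hypothesis 1.1 the plan uses a mixed model: "Subject will be the clustering factor and it will be nested within therapy group which will also be considered random". Primary Hypothesis 1.2 (arm on TRT) and Secondary Hypothesis 1.1 (arm on heart rate, skin conductance and DERS-S) follow the same strategy. The correlations in Secondary Hypothesis 1.2 are not said to. The opening of Data Analyses makes yes/no medication use a statistical control in every analysis.

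**The concern.** A mechanism claim needs two links: MBSR changes the mediator, and the mediator is related to aggression. The plan estimates the first link across arms under Secondary Hypothesis 1.1. The second is examined only inside the MBSR arm, and no analysis joins them.

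Within one arm at one session, a correlation between reactivity and shock setting would appear if calmer people were simply less aggressive, with or without MBSR. The hypothesis speaks of decreases in TRT aggression, but nobody has an earlier TRT score, and within a single arm there is no comparison group to stand in for one. The heart rate and skin conductance changes are reactions to the script in that session, not changes from before to after treatment.

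At stake is how the pilot informs the planned larger trial. A positive correlation could be carried forward as support for a mechanism when the statistic does not respond to whether MBSR moved the mediator.

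**Working it through.** **Inputs.** Sample size: "We will enroll 60 veterans with PTSD" (Participants). Allocation: "after 6 participants are recruited, they will be randomly assigned using urn randomization procedures" (Randomization Procedures), so 60/6 = 10 groups. The ratio is not stated. I assume 5:5, giving 30 in MBSR; 4:6 to 6:4 would give 24 to 36. Alpha and sidedness are not stated; I assume 0.05, two-sided. The plan says "Clustering group effects can be measured by an intra-class correlation" but gives no value; I use 0 to 0.30. The plan states no power or detectable correlation for this hypothesis, so there is no figure to reproduce.

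**1. Does the within-arm correlation respond to mediation?** Let M = a × arm + e1 and Y = b × M + e2, with unit error variances and b = 0.44 (assumed). Within either arm, r = b/√(1 + b²) = 0.44/√1.1936 = 0.40, and a does not appear. The indirect effect is a × b:

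| Shift in mediator, a (SD) | Within-MBSR r | Indirect effect a × b |
|---|---|---|
| 0 | 0.40 | 0 |
| 0.5 | 0.40 | 0.5 × 0.44 = 0.22 |
| 0.8 | 0.40 | 0.8 × 0.44 = 0.35 |

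A large-sample simulation gave 0.407, 0.404 and 0.402 for the three correlations.

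**2. Precision of the association.** By Fisher z, power ≈ Φ(atanh(r) × √(n − 3) − 1.96), with atanh(0.35) = 0.365.
- n = 30: 0.365 × √27 = 1.90; Φ(−0.06) = 0.48.
- n = 60: 0.365 × √57 = 2.76; Φ(0.80) = 0.79.

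The correlation detectable with 80% power is 0.49 at n = 30 (0.55 at 24, 0.45 at 36) and 0.36 at n = 60. These are simple correlations, before clustering, covariates, dropout or participants who withhold TRT data after debriefing.

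**3. Precision of the indirect effect.** I simulated 10 groups of 6, testing arm on mediator with group means and mediator on TRT by regression with arm in the model, and requiring both to be significant (b = 0.4 assumed):

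| a (SD) | ICC 0 | ICC 0.05 | ICC 0.10 |
|---|---|---|---|
| 0.5 | 0.36 | 0.29 | 0.25 |
| 0.8 | 0.67 | 0.59 | 0.52 |

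**4. Power of an arm × mediator check.** Separating r = 0.35 in one arm from r = 0 in the other, at 30 per arm: 0.365/√(2/27) = 1.34; Φ(1.34 − 1.96) = 0.27.

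**5. Clustering.** Simulated type I error of the Pearson test with 5 groups of 6:

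| ICC | Independent group effects | Same group effect in both variables |
|---|---|---|
| 0.05 | 0.052 | 0.056 |
| 0.10 | 0.054 | 0.080 |
| 0.20 | 0.068 | 0.16 |
| 0.30 | 0.093 | 0.30 |

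**6. Multiplicity.** Three mechanism variables × two TRT outcomes = 6 tests; 1 − 0.95⁶ = 0.26 if the tests were independent.

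**The case against.** The strongest defence is that the plan claims little here. Hypothesis 1.2 is worded as an association, the Overview speaks of potential mechanisms, and Sample Size and Power Considerations says the pilot may not reach significance and exists to plan a larger trial. The arm effects on the mediators and on the TRT are already tested across arms with therapy group random. A reader might infer that the plan has no controlled evidence on mechanism at all; Secondary Hypothesis 1.1 and Primary Hypothesis 1.2 show otherwise. What is missing is the step that joins them.

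The second objection also stands: a two-arm model does not fully cure the problem. The mediator is not randomised in either arm, so the mediator-TRT path stays open to confounding by individual differences, which baseline BPAQ only partly addresses. Pooling also assumes a common slope, which the within-arm analysis does not need, and the interaction check is weak at about 27% power.

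Three further inferences go too far:
- **Clustering invalidates the correlations.** Inflation is small up to an ICC of 0.10 unless the same group effect drives both variables. The firmer point is inconsistency with the plan's own model.
- **The false-positive risk is 26%.** That assumes independence, and these measures come from the same people in one session, so they are likely correlated. It is true that "Bonferroni adjustments will be implemented to control for Type 1 error" appears under Primary Hypothesis 1.1 and is not extended to the correlations.
- **The level-20 count is left wholly unattended.** Data Analyses plans normality screening and transformations, which cover it in part.

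**Conclusion.** The concern holds as a mismatch between the mechanism aim and the statistic chosen for it. The within-MBSR correlation cannot distinguish an indirect effect of 0 from 0.22 or 0.35, and the decreases in TRT aggression named in the hypothesis cannot be observed on the Table 1 schedule. The analysis also departs from the plan's therapy-group strategy and its medication rule.

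A reader might take the rise in power from 48% to 79% as the gain in testing mediation. It is not: it applies to a simple correlation of 0.35, at an assumed 30 per arm and two-sided 0.05. The indirect effect would have about 25% to 36% power at a = 0.5 SD, b = 0.4 and ICC 0 to 0.10, all assumed values. The gain is an imprecise estimate of the relevant quantity in place of a statistic that does not address it. This is an inexpensive improvement to a secondary pilot analysis; the primary comparisons are unaffected.

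**What to change.** 1. Fit the mediator-TRT association in all participants, adjusted for arm, baseline BPAQ and medication use, with therapy group random. State which heart rate and skin conductance score (response or recovery) is used.
2. Add an arm × mediator term and report it as a low-power check of the common slope.
3. Combine the association with the arm-to-mediator effect from Secondary Hypothesis 1.1, and report the indirect effect with a confidence interval, labelled exploratory.
4. Use a count model for the number of level-20 shocks.
5. Reword the hypothesis to say that lower reactivity and better emotion regulation are associated with lower TRT aggression.
6. Keep the within-MBSR correlations as descriptive only.
7. State both limits: the common-slope assumption and the non-randomised mediator.

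The cost is analysis-plan wording and a little analysis time. No new data are needed: both arms complete the same post-treatment session, and the BPAQ is already collected at baseline.
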